9.4. Treatment Compliance

The investigator or his/her designated and qualified representatives will only dispense study drug to patients enrolled in the study in accordance with the protocol. The study drug must not be used for reasons other than that described in the protocol. Patients who miss more than 42 doses (*i.e.*, 25% of the 168 expected doses) will not be considered treatment-compliant. Patients must be considered treatment-compliant to be eligible for the open-label extension study.

9.5. Randomization

An IWRS will be utilized to randomize patients 1:1 to bardoxolone methyl or placebo. Randomization will be stratified by number of background PAH therapies: 0, 1, or 2.

9.6. Blinding

In this double-blind study all patients, investigators, site personnel, laboratories and central readers with direct involvement in the conduct of the study or their designees will be blinded to treatment assignments. To prevent potential bias, appropriate measures will be taken to ensure the blind is maintained for the patients and personnel mentioned previously. To maintain the blind, investigators will distribute blinded study drug treatment kits to patients as directed by the IWRS system. Investigators and patients will not be blinded to dose level, but will be blinded to treatment assignment (*i.e.*, active study drug vs. placebo).

An IWRS system will manage treatment assignments. The only people with direct access to treatment assignments will be those individuals who develop and maintain the randomization code, the DSMB and the statistical group reporting to the DSMB.

9.6.1. Patient Unblinding

Although there is no known antidote to bardoxolone methyl, under rare circumstances unblinding may be considered medically necessary. The investigator is strongly encouraged to contact the medical monitor to discuss situations in which he or she believes that the blind should be broken, but ultimately the investigator has the right to break the blind (*e.g.*, in the event of a serious or life-threatening medical situation).

If unblinding is required, the investigator will utilize the IWRS to perform the unblinding. If a study drug assignment is unblinded, the investigator must describe the event that required unblinding in the patient's source documents.

Patients must discontinue taking study drug if their treatment assignment has been unblinded to the investigator (or designee). Such patients must undergo the same study drug discontinuation procedures as those patients who discontinue taking study drug for other reasons.

Patient treatment assignments must not be unblinded in the case of an AE or SAE, except as described above.

9.6.2. Unblinding for Regulatory Submission

In situations where regulation requires unblinding and reporting of a particular serious adverse event, the appropriate bodies (*e.g.*, ethics committees, IRBs, regulatory agencies) must be provided with unblinded information according to the applicable regulatory requirement. This information must not be conveyed to any investigator, site personnel or patient; therefore, this type of unblinding does not necessitate that the patient discontinue taking study drug. In cases when unblinded information must be conveyed to local health authorities, personnel without direct involvement in the conduct of the study must be responsible for unblinding the patient's treatment using the IWRS and conveying the necessary information.

9.6.3. Data Safety Monitoring Board

An independent Data Safety Monitoring Board (DSMB) will review unblinded safety data throughout the study and make recommendations as appropriate. The DSMB will begin quarterly data reviews approximately 3 months after the first patient is enrolled and continue through the last dose of the last patient enrolled.

The DSMB will consist of external experts supported by an independent statistical group. The independent statistical group will prepare unblinded analyses for the DSMB and will not have a role in the statistical analysis plan (SAP) after the study has started enrolling patients. A separate, blinded statistical group (*i.e.*, not associated with the DSMB) will be responsible for producing and finalizing the SAP and executing final data analysis of the study.

The DSMB will be governed by a charter that will describe the following:

- Roles and responsibilities of the DSMB members and the independent statistical group
- Meeting format and frequency
- Communication channels between the DSMB, the independent statistical group, the Sponsor, and the blinded study statisticians
- Voting process and requirements (*e.g.*, requirement of consensus for issuance of a termination recommendation)
- Provisions governing conflict of interest and confidentiality
- Process for interim analysis of efficacy, including the alpha spending function

Briefly, the DSMB will review the progress of the study and the accumulating unblinded data while the study is ongoing. The DSMB will make recommendations to Sponsor representatives following each meeting. The DSMB may recommend that the study continue as is, be modified to protect patient safety, or be terminated. However, investigators, and not the DSMB, will make intra-patient dose-escalation decisions at the Week 4 visit for each patient and may choose to decrease the patient's dose (to one-half of the prior dose).

9.7. **Unscheduled Visits**

Unscheduled visits are allowed for the following reasons:

- Assessment of weight gain per [Section 9.1.1](#);
- Management of an adverse event or serious adverse event;
- Performance of additional laboratory tests for clinically abnormal laboratory test values or to confirm a possible pregnancy;
- Dose de-escalation;
- Any time the investigator feels that it is clinically appropriate for patient safety.

At a minimum, unscheduled visits should include collection of adverse events, clinical chemistry, hematology, concomitant medications and vital signs, as well as collection/review of weight diary. Additional conversations may be necessary with the medical monitor following an unscheduled visit to assess patient safety.

9.8. **Pregnancy**

9.8.1. **Women of Childbearing Potential**

Women of childbearing potential (WOCBP) are those who are not surgically sterile (no history of bilateral tubal ligation, hysterectomy, or bilateral salpingo-oophorectomy) do not have fallopian inserts with confirmed blockage, have not had reproductive potential terminated by radiation, and are not postmenopausal for at least 1 year.

9.8.2. **Methods of Birth Control**

During Screening, while taking study drug and until 30 days following administration of the final dose of study medication, WOCBP must practice one of the following acceptable methods of birth control:

- Use double barrier contraception method defined as male use of a condom and female use of a barrier method (*e.g.*, contraceptive sponge, spermicidal jelly or cream, diaphragm [always use with spermicidal jelly/cream]);
- Use of hormonal contraceptives (oral, parenteral, vaginal, or transdermal) for at least 90 days prior to start of study drug administration;
- Use of an intrauterine device;

- Abstain from sexual intercourse completely. Complete abstinence from sexual intercourse is only acceptable if it is the preferred and usual lifestyle of the individual. Periodic abstinence is not permitted.

During Screening, while taking study drug and until 30 days after the final dose of study medication is taken, males who have female partners of childbearing potential must practice one of the following methods of birth control:

- Have had a vasectomy (at least 6 months earlier);
- Use double barrier contraception method, defined as male use of a condom and female use of a barrier method (*e.g.*, contraceptive sponge, spermicidal jelly or cream, diaphragm [always use with spermicidal jelly/cream]);
- Partner use of an intrauterine device;
- Partner use of hormonal contraceptives (oral, parenteral, vaginal or transdermal) for at least 90 days prior to start of study drug administration;
- Abstain from sexual intercourse completely. Complete abstinence from sexual intercourse is only acceptable if it is the preferred and usual lifestyle of the individual. Periodic abstinence is not permitted.

9.8.3. Suspected Pregnancy

During the study, all WOCBP must be instructed to contact the investigator immediately if they suspect they might be pregnant (*e.g.*, late or missed menstrual period). Male patients must be instructed to contact the investigator if a sexual partner suspects she may be pregnant.

If a patient or investigator suspects that the patient may be pregnant, the study drug must be withheld until the results of a serum pregnancy test are available. If the serum pregnancy test confirms the pregnancy, the patient must permanently discontinue taking study drug. The investigator must immediately report to the medical monitor a pregnancy associated with study drug exposure. The early discontinuation protocol-required procedures outlined for End-of-treatment and Follow-up visits must be performed on the patient.

Pregnancy is not considered an AE; however, the investigator must follow a pregnant patient, or the pregnant female partner of a male patient (if consenting), and report follow-up information regarding the course of the pregnancy, including perinatal and neonatal outcome. Infants resulting from such pregnancies should be followed for a minimum of 8 weeks. Reata or designee may contact the investigator to request additional information throughout the course of the pregnancy.

The following pregnancy outcomes must be considered SAEs and will require additional reporting in the eCRF and reported as a serious adverse event:

- Congenital anomaly/birth defect;
- Stillbirth;
- Spontaneous miscarriage.

9.9. Serious Toxicities

In the case of serious toxicities, the investigator may choose to interrupt treatment with bardoxolone methyl. Dose reductions are permitted to manage tolerability issues. Dose escalations are not permitted beyond the scheduled Week 4 visit. Once a patient's dose has been reduced, that dose should be maintained until the Week 24 visit. Patients who resume therapy after an interruption will follow the originally planned study schedule.

9.10. Study Procedures

The following sections describe each assessment. The timing of these assessments is noted in [Table 3](#). All Day 1 procedures, except AE assessments, should be completed prior to administration of first dose of study drug.

9.10.1. Informed Consent

Written informed consent (see [Section 15.3](#)) must be obtained from the patient before any study-related procedures are performed, and again if there is a change in the study procedures that would affect the patient's willingness to participate.

9.10.2. Inclusion/Exclusion

Inclusion and exclusion criteria must be reviewed as indicated in [Table 3](#). Patients must meet all of the inclusion and none of the exclusion criteria for entry in the study. Investigators should contact the medical monitor with any questions regarding eligibility prior to randomizing the patient on Day 1.

9.10.3. Demographics and Baseline Disease Characteristics

Demographic data including sex, age, race, and ethnicity, will be collected as indicated in [Table 3](#). Baseline disease characteristics will be collected as indicated in [Table 3](#).

9.10.4. Prior and Current Concomitant Medications

The name, dose, and frequency must be recorded for all medications that the patient is taking. All allowed and excluded medications should be recorded including all prescription drugs, herbal products, vitamins, minerals, and over-the-counter medications. Trade or generic drug names should be used where possible. Concomitant medications will be reviewed as indicated in [Table 3](#) and all changes will be recorded.

9.10.5. Current PAH Background Medications

The name, dose, and frequency must be recorded for all PAH background medications that the patient is taking. PAH background medications are those that have been approved by the FDA or the local health authority for the treatment of PAH. Trade or generic drug names should be used where possible. PAH background medications will be reviewed as indicated in [Table 3](#) and all changes will be recorded. Additional background PAH medications may only be prescribed after a clinical worsening event is confirmed.

9.10.6. Medical History

A complete medical history (*e.g.*, per patient report) that includes all medical history within the past 5 years must be collected. Medical history will be recorded as indicated in [Table 3](#).

9.10.7. Height

Height should be measured without footwear or prosthetics as indicated in [Table 3](#).

9.10.8. Echocardiogram

If an echocardiogram has not been performed within 90 days of Day 1, an echocardiogram must be performed during Screening to confirm eligibility as indicated in [Table 3](#).

9.10.9. Weight and Body Mass Index (BMI)

Weight must be measured as indicated in [Table 3](#). Body mass index (BMI) will be calculated in the eCRF each time the weight is recorded. The Sponsor will provide each patient with a scale to use at home to measure weight, and a diary will be provided to record the at-home weight measurements and the self-administration of study drug. Weights recorded in patient diaries will not be entered in the eCRF. Weights should be taken at the same time each day and recorded in a patient diary. During the first eight weeks, weights will be recorded daily; weekly weights will be recorded thereafter. Patients will be instructed to stop administering study drug and contact the investigator if their daily weight increases per the criteria outlined in [Section 9.1.1](#). Patients will be provided instructions within the Informed Consent Form to help ensure consistent weight collection throughout the study.

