5.1.2. Fluid Overload

Similar to endothelin receptor antagonists (ERAs) in certain patient populations, including bosentan in advanced congestive heart failure and avosentan in advanced CKD, bardoxolone methyl treatment was found to be associated with an increased risk for fluid overload and heart failure hospitalizations in the BEACON trial, which enrolled patients with Stage 4 CKD (eGFR 15-29 mL/min/1.73 m²) and type 2 diabetes. The overall increased risk for fluid overload and heart failure events with bardoxolone methyl appeared to be limited to the first three to four weeks after initiation of treatment. Elevated BNP and prior hospitalization for heart failure were identified as risk factors that contributed to increased risk for these events. The increased risk for these events from bardoxolone methyl treatment had not been observed in six previous CKD studies, which were conducted mostly in patients with Stage 3b CKD (eGFR of 30-44 mL/min/1.73 m²), patients with hepatic dysfunction, cancer patients, or healthy volunteers.

Review of admission notes and narrative descriptions for heart failure hospitalizations in BEACON indicates that heart failure in bardoxolone methyl-treated patients was often preceded by rapid fluid weight gain (several kilograms within the first weeks of treatment initiation) and was not associated with acute renal decompensation or acutely reduced left ventricular contractility. Available data from BEACON and other studies suggest that bardoxolone methyl treatment can differentially affect hemodynamic status according to the clinical condition of patients and likely promotes fluid retention in patients with more advanced renal dysfunction and other recognized risk factors associated with heart failure at baseline.

In a Phase 2 dose-ranging study of the efficacy and safety of bardoxolone methyl in patients with pulmonary hypertension (LARIAT), risk mitigation procedures were employed to reduce the potential for bardoxolone methyl-induced fluid overload; these procedures excluded patients with the identified risk factors and ensured close monitoring for fluid retention within the first month of treatment. To date, the risk for acute fluid overload adverse events with bardoxolone methyl in late-stage CKD patients has not been observed in PAH patients.

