5.1.5. Weight Loss

Decreases in weight and reports of anorexia/decreased appetite have been observed following treatment with bardoxolone methyl in patients with CKD who also had type 2 diabetes. In studies of these patients, 17% of bardoxolone methyl patients reported adverse events of weight decrease or decreased appetite (irrespective of relationship to treatment). Weight reduction was more pronounced in patients treated with bardoxolone methyl than in those given placebo.

Weight loss of approximately one kilogram per month was observed, with patients of higher body-mass index at baseline losing more weight (in absolute terms) than those of normal or moderately-elevated body-mass index.

Bardoxolone methyl-treated PAH patients have also had decreases in weight, with mean weight decreases of approximately 3 kg versus placebo at Week 16. Weight loss in PAH patients has not coincided with reports of decreased appetite or anorexia adverse events.

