9.1.1. Management of Fluid Status

Specific risk mitigation procedures will be employed to reduce the potential for bardoxolone methyl-induced fluid overload. These procedures include exclusion of patients with any clinically significant renal disease, defined as an eGFR value of $< 45 \text{ mL/min/1.73 m}^2$. To exclude patients with significant cardiac dysfunction, the study will exclude patients with a history of left-sided heart disease. Patients who have evidence of volume overload at baseline, defined as BNP level of $> 400 \text{ pg/mL}$, will also be excluded. Laboratory data will also be used to monitor fluid status after randomization.

Additionally, after randomization patients will be closely monitored for rapid weight gain suggestive of fluid overload. Patients will be given a Sponsor-provided scale to use at home to collect and record their weights daily during the first 8 weeks of the treatment period and weekly thereafter. Patients who experience a five-pound (2.3 kilogram) or greater increase in weight since their Day 1 weight during the first 8 weeks of the study will be instructed to stop taking their study medication immediately and return to the clinic for an unscheduled physical examination and laboratory assessment by the investigator. Patients who experience a five pound (2.3 kilogram) or greater increase in weight between Day 1 and Week 8 may not restart their study medication until the investigator has completed and documented an assessment of fluid overload.

Patients who experience a five pound (2.3 kilogram) or greater increase in weight after the Week 8 study visit will be instructed return to the clinic for an unscheduled physical examination and laboratory assessment by the investigator. Study medication should not be discontinued unless the investigator has completed and documented an assessment of fluid overload and determines that the patient should be discontinued.

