12.5.2. Weight

Weight change from baseline will be summarized by baseline BMI category (< 18.5, 18.5 to < 25.0, 25.0 to < 30.0, 30.0 or greater).

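### The home weights behind the 2.3 kg stop are not captured for analysis and no visible table counts the trigger by arm, so mean weight change can mask early gains in a minority

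*Protocol*

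**What the plan says.** **The signal.** Protocol 5.1.2 reports that heart failure on bardoxolone methyl in the earlier Stage 4 CKD trial often followed a gain of several kilograms soon after starting treatment. The excess risk appeared confined to the first three to four weeks. The same section says this risk had not been observed in PAH patients to date.

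**The trigger.** Protocol 9.1.1 acts on a "five-pound (2.3 kilogram) or greater increase in weight since their Day 1 weight during the first 8 weeks of the study": the patient stops drug at once, returns for an unscheduled examination and laboratory assessment, and may not restart until the investigator has documented a fluid-overload assessment. On home weighing, 9.10.9 says: "During the first eight weeks, weights will be recorded daily; weekly weights will be recorded thereafter".

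**What is captured.** Also in 9.10.9: "Weights recorded in patient diaries will not be entered in the eCRF". For the return visit, 9.7 sets this least content: "unscheduled visits should include collection of adverse events, clinical chemistry, hematology, concomitant medications and vital signs, as well as collection/review of weight diary". Vital signs (9.10.11) are heart rate, respiration, temperature and blood pressure. The physical examination (9.10.12) does not list weight either. Table 3 schedules clinic weights at Screen A, Day 1 and Weeks 1, 2, 4, 6, 8, 16, 24 and 28.

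**What is analysed.** SAP 12.5 summarizes actual weights and changes by arm at scheduled visits. SAP 12.5.2 adds: "Weight change from baseline will be summarized by baseline BMI category". Continuous summaries give n, mean, median, SD, minimum and maximum (SAP 5). Baseline is in general the mean of pre-dose values (SAP 5.1).

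**The opposing trend.** Protocol 5.1.5 reports "mean weight decreases of approximately 3 kg versus placebo at Week 16" in PAH patients.

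**The concern.** Weight is a named safety endpoint (Protocol 6.2.4), and the secondary objective is safety relative to placebo. The protocol defines its own early-warning event, but that event is not carried into the planned analysis: the triggering weight stays in the diary, the confirming clinic weight is optional, and no visible table counts threshold gains or drug holds for weight gain.

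Two separate problems follow. A gain that appears and resolves between scheduled visits reaches at most a listing. A gain that persists to a scheduled visit enters a mean that drug-related weight loss is pulling the other way. At stake is whether the report can say how often the trigger fired on bardoxolone methyl compared with placebo.

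**Working it through.** The documents give no figure for this point to reproduce. The check is a trace of the data, followed by an illustration.

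**1. Threshold.** 5 lb × 0.45359 = 2.268 kg, which rounds to the stated 2.3 kg.

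**2. Density of information.** In the first 8 weeks there are 8 × 7 = 56 planned home weights and 5 post-baseline clinic weights (Weeks 1, 2, 4, 6, 8), and 5/56 = 9%. Over 24 weeks there are 56 + 16 = 72 home weights and 7 clinic weights, and 7/72 = 10%.

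**3. A transient gain.** Take a patient who triggers on Day 17 and whose site chooses to weigh them.
- SAP Appendix D puts Day 17 in the Week 2 window (Days 11 to 21, target Day 14), 3 days from target.
- SAP 5.2.2 keeps the measurement closest to target and, in a tie, the earlier one.
- A Week 2 visit made before Day 17 and within its allowed Day 14 ± 3 is at most 3 days from target, so it is kept and the Day 17 weight is not tabulated. It therefore cannot appear as a maximum. SAP 5.2 would list it.
- If the site did not weigh the patient, the database holds no weight from that day.

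**4. Baseline.** Let S be the Screen A weight, D the Day 1 clinic weight and W a later clinic weight. The SAP change is W − (S + D)/2 = (W − D) − (S − D)/2. Screening may precede Day 1 by up to 90 days. If S − D were 1 kg (an assumption), a gain of 2.3 kg over Day 1 would be tabulated as 1.8 kg. The Day 1 clinic weight is collected, so this can be corrected in analysis.

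**5. Masking of a persistent gain (illustration).** Assumptions: the 3 kg difference at Week 16 builds up linearly, so L = 3 × week/16; unaffected patients lose L; affected patients show a net gain G. A share p of gainers gives an arm mean of pG − (1 − p)L, which is zero at p = L/(L + G).

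| Visit | L (kg) | Break-even p, G = 3 kg |
|---|---|---|
| Week 2 | 0.375 | 0.375/3.375 = 11% |
| Week 4 | 0.75 | 0.75/3.75 = 20% |
| Week 8 | 1.5 | 1.5/4.5 = 33% |

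At Week 4, G = 2.3 kg gives 0.75/3.05 = 25% and G = 5 kg gives 0.75/5.75 = 13%. With 65 patients per arm (SAP Appendix B.2), the Week 4 mean reaches zero at 13 gainers: (13 × 3 − 52 × 0.75)/65 = 0.

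**6. Mean against threshold count.** Assume that at Week 4, 10% of the active arm retains 4 kg of fluid on top of a 0.75 kg loss, placebo has mean change zero, and change is normal within each subgroup. The mean difference is −0.75 + 0.10 × 4 = −0.35 kg, which reads as weight loss. The share at or above +2.3 kg depends on the assumed SD:

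| SD (kg) | Active | Placebo |
|---|---|---|
| 1.0 | 8.4% | 1.1% |
| 1.5 | 9.3% | 6.3% |
| 2.0 | 12.6% | 12.5% |

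The threshold count shows the excess when weight is stable, but not when ordinary variation is large. At Week 2 the mean difference in the same scenario is −0.375 + 0.40 = about +0.03 kg, so masking is weaker there.

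**The case against.** A reader might infer that the plan hides fluid overload from the safety objective altogether. The documents do not support that. The objective also covers adverse events, serious adverse events, examinations and laboratory values (SAP 2.1.2). Diuretic changes must go into the eCRF (Protocol 9.3.2), BNP and NT-proBNP are drawn at every in-person visit (Table 3), edema and fluid retention are reviewed in aggregate (11.7), and the DSMB sees unblinded safety data (9.6.3).

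Nor do the weight tables show change alone. They include actual values with SD, minimum and maximum, so a large gain present at a scheduled visit would show. Clinic weights at Weeks 1, 2 and 4 fall within the stated risk period. The return visit reviews the diary, and the fluid assessment must be documented. Calling this the main risk in the present population also goes too far, given what 5.1.2 says about PAH patients. Finally, Table 3 has sites collect the diaries, so a comparison by arm is unplanned rather than impossible.

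All of that stands and narrows the point, but it does not supply the count. No rule makes a triggered gain an adverse event, and Protocol 11.6 says accompanying signs are not recorded separately from a diagnosis. SAP 12.2 summarizes events leading to study discontinuation, SAP 7.2 covers permanent drug discontinuation, and SAP 8.2 counts missed doses without reasons; a temporary hold for weight gain appears in none of these as such. BNP is not named in SAP Appendix E, although that list allows further tests.

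**Conclusion.** The point holds in a limited form. As planned, the frequency of the 2.3 kg trigger and of weight-triggered drug holds is not compared by arm. A resolved gain reaches at most a listing, and mean change can conceal a minority of gainers.

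The masking figures of about 11% at Week 2 and 20% at Week 4 are illustrative. They rest on linear loss, on a net 3 kg gain still present at the visit, and on using a placebo-adjusted whole-group mean as the loss of unaffected patients. The documents give neither the proportion affected nor the SD of weight change. The capture gap depends on none of these assumptions.

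The primary endpoint is unaffected. The exploratory sections are redacted and the DSMB charter is a separate document, so a further weight or fluid analysis there can be neither confirmed nor excluded. This is an inexpensive improvement to the reporting of a named safety endpoint, not a failure of safety monitoring.

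**What to change.** 1. **eCRF and Protocol 9.7, 9.10.9.** For each trigger, enter one home weight and its date, with the Day 1 home weight as comparator (Table 3 already schedules it). Record a clinic weight at unscheduled visits made for weight gain. The rest of the diary can stay out of the database.
2. **SAP 12.5.2.** Add a by-arm table of the number and percentage of patients with a gain of 2.3 kg or more over Day 1 at any scheduled or unscheduled assessment through Week 8. Compare clinic weights with the Day 1 clinic weight and home trigger weights with the Day 1 home weight, so that the two scales are not mixed. Add the number of patients whose drug was held for weight gain.

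The cost is one short eCRF entry per trigger, one weighing at a visit that already takes place, and one table. The scheduled-visit part of the table needs only clinic weights already collected. The clinical stop rule is not changed.
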